# 10.2 Causality Assessment

For every unsolicited AE, an assessment of the relationship of the event to the administration of the vaccine will be undertaken by the CI or the CI-delegated clinician at the coordinating site (Oxford). An intervention-related AE refers to an AE for which there is a possible, probable or definite relationship to administration of a vaccine. An interpretation of the causal relationship of the intervention to the AE in question will be made, based on the type of event; the relationship of the event to the time of vaccine administration; and the known biology of the vaccine therapy (Table 3).

Causality assessment will take place during planned safety reviews, interim analyses (e.g. if a holding or stopping rule is activated) and at the final safety analysis, except for SAEs, for which causality should be assigned by the clinically trained reporting Investigator.

0	No Relationship	No temporal relationship to study product and Alternate aetiology (clinical state, environmental or other interventions); and Does not follow known pattern of response to study product
1	Unlikely	Unlikely temporal relationship to study product and Alternate aetiology likely (clinical state, environmental or other interventions) and Does not follow known typical or plausible pattern of response to study product.

2	Possible	Reasonable temporal relationship to study product; or Event not readily produced by clinical state, environmental or other interventions; or Similar pattern of response to that seen with other vaccines
3	Probable	Reasonable temporal relationship to study product; and Event not readily produced by clinical state, environment, or other interventions or Known pattern of response seen with other vaccines
4	Definite	Reasonable temporal relationship to study product; and Event not readily produced by clinical state, environment, or other interventions; and Known pattern of response seen with other vaccines

**Table 3:** Guidelines for assessing the relationship of vaccine administration to an AE.

### 10.3 Reporting Procedures for all AEs

All AEs occurring in the 28 days following each vaccination observed by the Investigator or reported by the volunteer, whether or not attributed to the study vaccine, will be recorded. Recording and reporting of all AEs will take place as detailed in SOP VC027. We will not record bruising due to blood-taking or cannulation. All AEs that result in a volunteer's withdrawal from the study will be followed up until a satisfactory resolution occurs, or until a non-study related causality is assigned (if the volunteer consents to this). SAEs will be collected throughout the entire trial period. For each participant, this means the safety reporting window per participant (from provision of study consent to final follow-up visit).

Each AE will be graded by the participant according to the table for grading severity of AEs (see Table 4). Severity gradings may be reviewed and discussed with the participants at the clinic visits. Volunteers will be instructed on how to self-assess the severity of these AEs. There will also be space on the e-diary to self-document unsolicited AEs, and whether medication was taken to relieve the symptoms.

The severity of clinical AEs will be assessed by the Investigators according to the scales in Tables 4-6. Severity grading for laboratory AEs are dependent on the Oxford University Hospitals laboratory's reference and will be graded according to the scales in the site-specific table that can be found in the Trial Master File (TMF). These ranges will be based on FDA guidance relative to local laboratory reference ranges [https://www.fda.gov/media/73679/download].

Grade	Severity			
GRADE 0	None			
GRADE 1	Mild: Transient or mild discomfort (< 48 hours); no medical intervention/therapy required			
GRADE 2	Moderate: Mild to moderate limitation in activity – some assistance may be needed; no or minimal medical intervention/therapy required			
GRADE 3	Severe: Marked limitation in activity, some assistance usually required; may require medical intervention/therapy			

Table 4: Severity grading criteria for AEs.

Physical Observations	Grade 1	Grade 2	Grade 3
Tachycardia – beats per min*	101-115	116-130	>130
Hypotension (systolic) mm Hg	85-89	80-84	<80
Hypertension (systolic) mm Hg**	141-159	160-179	≥180
Hypertension (diastolic) mm Hg**	91-99	100-109	≥110
Fever °C	37.6 – 38.0	38.1-39.0	>39.0

Table 5: Severity grading criteria for clinically significant abnormal physical observations. All observations should be measured at rest. \*Only applies when resting heart rate is between 60 and 100 beats per minute. Use clinical judgement when characterising bradycardia in some healthy participant populations (e.g. conditioned athletes). \*\*Systolic or diastolic hypertension may only be confirmed as clinically significant (and therefore an AE) if persistently present when observations are repeated (i.e. isolated measurements of hypertension are not clinically significant).

Adverse Event	Grade	Intensity
Pain at injection site	1	Pain that is easily tolerated
	2	Pain that interferes with daily activity
	3	Pain that prevents daily activity

Erythema at injection site	1	>3 - ≤50 mm
	2	>50 - ≤100 mm
	3	>100 mm
Swelling at injection site*	1	>3 - ≤20 mm
	2	>20 - ≤50 mm
	3	>50 mm

**Table 6:** Severity grading criteria for local adverse events. \*Erythema or swelling ≤3mm is an expected consequence of skin puncture and will therefore not be considered an adverse event.

# **10.4 Reporting Procedures for SAEs**

This will be conducted in accordance with the SOP OVC005 Safety Reporting. In order to comply with current regulations on SAE reporting to regulatory authorities, the event will be documented accurately and notification deadlines respected. SAEs will be reported on the SAE forms to members of the study team immediately after the Investigators become aware of their occurrence, as described in SOP OVC005. Copies of all reports will be forwarded for review to the CI (as the Sponsor's representative) within 24 hours of the Investigator being aware of the suspected SAE. The Local Safety Monitor (LSM) will be notified of SAEs which are deemed possibly, probably or definitely related to study interventions; the LSM will be notified immediately (within 24 hours) of the Investigators' being aware of their occurrence. SAEs will not normally be reported immediately to the REC unless there is a clinically important increase in occurrence rate, an unexpected outcome, or a new event that is likely to affect safety of trial volunteers, at the discretion of the CI and/or LSM. In addition to the reporting above, the Investigator shall include all SAEs in the annual Development Safety Update Report (DSUR) report.

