## 7.3 Study overview

This is an open-label, single-centre, non-randomised, first-in-human Phase Ia study to assess the safety and immunogenicity of the Pfs48/45 vaccine, administered with Matrix-M adjuvant.

Up to 30 healthy, malaria-naïve adults aged between 18 and 45 years will be recruited into one of three groups (n=8-10 per group) at the Centre for Clinical Vaccinology and Tropical Medicine (CCVTM), Oxford over approximately 12 months.

All volunteers will receive three doses of Pfs48/45 at 10  $\mu$ g or 50  $\mu$ g, in 50  $\mu$ g Matrix-M, administered intramuscularly and given four weeks apart. Enrolment will be staggered. Initially, a single volunteer from Group 1 will receive the first vaccination alone, followed by clinical review on the day after vaccination and further monitoring via a diary card for at least a further 24 hours. Provided there are no safety concerns, a further two volunteers from Group 1 may then be vaccinated, at least 1 hour apart. Following review of the second and third volunteers at the 48-hour timepoint, an internal safety review will be conducted. If no safety concerns are identified, the remaining volunteers in the group will be vaccinated. The staggered enrolment process will be repeated for Group 2 for the first three volunteers. Following this, recruitment to Groups 2 and 3 will occur in parallel.

Volunteers will attend regular follow-up visits after each of the three vaccinations and will self-report AEs in the post-vaccination period via a diary card. Blood will be taken at regular intervals to assess safety outcomes via laboratory adverse events, as well as the immune response to vaccination. Volunteers will be followed until approximately 8 months from the time of enrolment.

All vaccinations and follow-up visits will be performed at the CCVTM in Oxford.

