## 10.1.4 Serious Adverse Reaction (SAR)

An AE (expected or unexpected) that is both serious and, in the opinion of the reporting Investigator or Sponsors, believed to be possibly, probably or definitely due to an IMP or any other study treatments, based on the information provided.

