# **10.4.1 Reporting Procedures for SUSARS**

The CI will report all SUSARs to the MHRA and REC within required timelines (15 days for all SUSARs, unless life-threatening or fatal. Fatal and life-threatening SUSARs will be reported to the MHRA and REC no later than 7 calendar days after the Sponsor or delegate is first aware of the reaction. Any additional relevant information will be reported within 8 calendar days of the initial report. All other SUSARs will be reported within 15 calendar days of awareness. The CI will also inform all Investigators concerned of relevant information about SUSARs that could adversely affect the safety of participants.

All SUSARs and deaths occurring during the study will be reported to the Sponsor. For all deaths, available autopsy reports and relevant medical reports will be made available for reporting to the relevant authorities.

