# 10.8 Local Safety Monitor

The LSM will be appointed to provide real-time safety oversight. The LSM will review SAEs deemed possibly, probably or definitely related to study interventions. The LSM will be notified within 24 hours of the Investigators' being aware of their occurrence. The LSM has the power to terminate the study if deemed necessary following a study intervention-related SAE. At the time of writing, the LSM is [name], a Clinical Tutor in Medicine, Honorary Consultant Physician and Director, Centre for Tropical Medicine at the University of Oxford. All correspondence between the Investigator and the LSM will be conveyed by the Investigator to the trial Sponsor on their request.

The LSM may be contacted for advice and independent review by the Investigator or trial Sponsor in the following situations:

- Following any SAE deemed to be possibly, probably, or definitely related to a study intervention
- Any other situation where the Investigator or trial sponsor feels independent advice or review is important.

The study can be put on hold upon advice of the LSM, CI, study sponsor or Ethical Committee(s), for any single event or combination of multiple events which, in their professional opinion, jeopardise the safety of the participants or the reliability of the data. If the study is placed on hold it may only be restarted following discussion with and approval from the LSM, the ethics committee(s), the trial Sponsor, the MHRA and CI.

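### The Local Safety Monitor is routinely told only of SAEs already judged related, so an SAE or AESI labelled unrelated has no required real-time route to the person appointed for real-time safety oversight

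*Combined protocol and SAP*

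**What the plan says.** Section 7.3 describes the trial: "This is an open-label, single-centre, non-randomised, first-in-human Phase Ia study". Between 24 and 30 volunteers each receive three vaccinations and are followed to day 240.

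The following provisions govern what happens to an SAE.

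- **Who judges causality.** Under 10.2, causality of unsolicited AEs "will be undertaken by the CI or the CI-delegated clinician at the coordinating site", at planned safety reviews, interim analyses and the final analysis, "except for SAEs, for which causality should be assigned by the clinically trained reporting Investigator".
- **Who tells the LSM, and of what.** Section 10.4: "The Local Safety Monitor (LSM) will be notified of SAEs which are deemed possibly, probably or definitely related to study interventions", within 24 hours. Section 10.8: "The LSM will review SAEs deemed possibly, probably or definitely related to study interventions".
- **What the judgement decides.** An SAE at least possibly related triggers a group hold (10.9.1) and an individual stop (10.9.2), and is reported as a SUSAR (10.1.5).
- **AESIs.** Section 10.6 reports these as SAEs, so they pass through the same filter.
- **What the LSM is for.** Section 10.8 appoints the LSM to give real-time oversight and lets a hold follow the LSM's advice on any single event or combination of events. Section 10.4 gives the CI and/or the LSM discretion over prompt REC reporting, for example when SAEs become more frequent.
- **Who else sees SAEs.** All SAE reports go to the CI within 24 hours (10.4), and SAEs are notified to the Sponsor (13.3). Section 10.4.1 adds: "All SUSARs and deaths occurring during the study will be reported to the Sponsor". The adjuvant manufacturer is provided with SAE reports (10.9.1).

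**The concern.** One error that safety oversight in a first-in-human study should be able to catch is an SAE that is related to the vaccine but has been labelled unrelated. The LSM's routine input is selected by the very judgement that may be wrong. A correct label costs nothing. If the label is wrong, the SAE hold, the SAE stop and SUSAR reporting do not operate, and the protocol does not require that the LSM be told.

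The limit also restricts functions that the protocol gives the LSM elsewhere. An LSM cannot advise a hold on an event that was never sent. An LSM who sees only SAEs labelled related cannot judge whether SAEs as a whole are becoming more frequent, which is one of the grounds for prompt REC reporting under 10.4.

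The AESIs sharpen the point. A new suspected autoimmune or chronic inflammatory disease may appear late in the 240 days of follow-up, when its timing relative to vaccination is most open to argument.

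**Working it through.** The documents give no figure for this process, so the main check is a reading of every causality, SAE, LSM, holding, stopping and SUSAR provision.

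**Step 1: which rules depend on a causality judgement?**

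| Rule | Needs a relatedness call? |
|---|---|
| Group hold, solicited local (10.9.1) | No |
| Group hold, solicited systemic (10.9.1) | No |
| Group hold, unsolicited Grade 3 (10.9.1) | Yes |
| Group hold, SAE (10.9.1) | Yes |
| Individual stop, local reaction (10.9.2) | No |
| Individual stop, laboratory AE (10.9.2) | Yes |
| Individual stop, solicited systemic (10.9.2) | Yes |
| Individual stop, unsolicited Grade 3 (10.9.2) | Yes |
| Individual stop, allergic reaction (10.9.2) | No |
| Individual stop, SAE (10.9.2) | Yes |

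Group holds: 2 of 4 depend on it. Individual stops: 4 of 6. Together 6 of 10 do and 4 of 10 do not. For an SAE as such, all three consequences (group hold, individual stop, SUSAR) depend on it.

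**Step 2: how can an SAE labelled unrelated reach the LSM?**

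| Route | Required? | Real time? | Limit |
|---|---|---|---|
| LSM notification (10.4, 10.8) | Not for these SAEs | – | Related SAEs only |
| LSM consulted in any other situation (10.8) | No | Possible | Only if the Investigator or Sponsor thinks it important |
| LSM review before dose escalation (7.4.2) | Yes | No | Once, before Groups 2 and 3; SAEs are not among the data named, though the list is not closed |

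The staggered-dosing reviews that continue into Group 2 (7.4.1) are by the CI with the Lead Clinician. No LSM review is scheduled after 50 µg dosing begins.

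**Step 3: who else receives such an SAE?** The CI and the Sponsor receive it promptly, and 10.1.4 defines a serious adverse reaction as one "in the opinion of the reporting Investigator or Sponsors, believed to be possibly, probably or definitely due to an IMP", so the Sponsor may judge an event related when the Investigator has not. However, 10.4 has the CI receive SAE reports as the Sponsor's representative, and under 10.2 the CI also assigns or delegates causality for unsolicited AEs. The adjuvant manufacturer receives SAE reports, but under a confidential agreement whose timing and review duties the protocol does not give. The safety update report (10.5) includes all SAEs but is annual, against about 8 months of follow-up per volunteer.

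**Step 4: how many extra notifications would full reporting bring?** The SAE rate is an assumption, because the documents give none.

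Person-years = volunteers × 240 / 365:

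- 24 × 240 / 365 = 15.8
- 30 × 240 / 365 = 19.7

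Expected SAEs of any causality = person-years × rate:

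| Assumed SAEs per 100 person-years | 24 volunteers | 30 volunteers |
|---|---|---|
| 1 | 15.8 × 0.01 = 0.16 | 19.7 × 0.01 = 0.20 |
| 5 | 15.8 × 0.05 = 0.79 | 19.7 × 0.05 = 0.99 |
| 20 | 15.8 × 0.20 = 3.2 | 19.7 × 0.20 = 3.9 |

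These counts are ceilings on the extra notifications, since SAEs called related already go to the LSM.

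**The case against.** The case against has real weight.

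- **Checks exist outside the reporting Investigator.** The CI and Sponsor see all SAEs, the Sponsor can judge one related, every death reaches the Sponsor, and the manufacturer is provided with SAE reports. A reader might infer that the Investigator's call has no second look at all. The documents do not support that. What stands is narrower: none of these routes is a required, real-time route to the LSM.
- **Many rules do not use causality.** A reader might infer that this one judgement controls all holds and stops. It does not: 4 of the 10 rules need no such call, and 10.8 allows a hold for any event judged to jeopardise safety. The dependence is complete only for the rules specific to SAEs.
- **The bar for Possible is low.** In Table 3 the criteria for Possible are joined by *or*, so reasonable timing alone is enough, while Unlikely needs all of its criteria. Applied strictly, the table makes mislabelling of an event soon after vaccination less likely. It helps less where the timing itself is in dispute.
- **Escalation is protected.** Under 7.4.2 no 50 µg dose is given until the LSM has approved a safety report that is not filtered by causality. A reader might infer that the trial could move to 50 µg without LSM scrutiny; it could not. The gap lies mainly after that step.
- **Open label adds little.** Every volunteer receives active vaccine, so blinding to dose would not hide exposure. The point does not rest on it.
- **Sections 10.4 and 10.8 agree on the filter, and SOP OVC005, which governs SAE reporting, is not available here.** The SOP may add steps. The protocol's own text on the LSM is nevertheless explicit, and the tension lies within 10.8, between the LSM's role and what the LSM is sent.

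**Conclusion.** The point holds as a gap in notification scope. The LSM is routinely sent only SAEs that have already been called related. For SAEs and AESIs that call also decides the group hold, the individual stop and SUSAR reporting, and no provision requires the LSM to see the remainder in real time.

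The size is modest. Other parties see these SAEs, the trial is small, and the expected count is about 0.2 to 1 at the assumed 1 to 5 per 100 person-years, or about 3 to 4 at an assumed 20. These figures show only that the remedy is inexpensive. A reader might take them as an estimate of harm, but harm requires an SAE that is both truly related and mislabelled, and the documents give nothing from which to estimate that fraction.

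The conclusion rests on the protocol text alone and assumes that SOP OVC005 and the manufacturer's safety agreement do not already send every SAE to the LSM. It is a cheap improvement.

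**What to change.** Amend 10.4 and 10.8 so that the LSM is notified within 24 hours of every SAE and AESI, whatever the assigned causality, with the Investigator's assessment attached so that the LSM can comment on it.

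In the same amendment, the sponsor should reconcile the LSM's notification scope with the oversight role in 10.8, and state how differing causality opinions between the Investigator, the Sponsor and the LSM are handled and recorded. The effect of a difference on holding or stopping is for the sponsor to settle; no such rule is proposed here. If SOP OVC005 already provides for full notification, the protocol text should be aligned with it.

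The cost is a few sentences in an amendment and, on the assumptions above, about one extra notification or fewer in the trial (3 to 4 at the highest assumed rate). The LSM is already part of the design, so no new staff are needed.

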# **10.4.1 Reporting Procedures for SUSARS**

The CI will report all SUSARs to the MHRA and REC within required timelines (15 days for all SUSARs, unless life-threatening or fatal. Fatal and life-threatening SUSARs will be reported to the MHRA and REC no later than 7 calendar days after the Sponsor or delegate is first aware of the reaction. Any additional relevant information will be reported within 8 calendar days of the initial report. All other SUSARs will be reported within 15 calendar days of awareness. The CI will also inform all Investigators concerned of relevant information about SUSARs that could adversely affect the safety of participants.

All SUSARs and deaths occurring during the study will be reported to the Sponsor. For all deaths, available autopsy reports and relevant medical reports will be made available for reporting to the relevant authorities.

# 10.5 Development Safety Update Report

The CI will submit (in addition to the expedited reporting above) DSURs once a year throughout the clinical trial, or on request, to the Competent Authority (MHRA in the UK, Ethics Committee, HRA, Host NHS Trust and Sponsor).

### 10.6 AEs of Special Interest

AEs of special interest will be reported as SAEs. These are:

- Severe hypersensitivity reactions (e.g. anaphylaxis)
- Any new, suspected autoimmune or chronic inflammatory disease

### 10.7 Procedures to be followed in the event of abnormal findings

Eligibility for enrolment in the trial in terms of laboratory findings will be assessed as detailed in SOP VC027. Abnormal clinical findings from medical history, examination or blood tests will be assessed as to their clinical significance throughout the trial. Laboratory AEs will be assessed using the site-specific tables in the TMF. If a test is deemed clinically significant, it may be repeated, to ensure it is not a single occurrence. If a test remains clinically significant, the volunteer will be informed and appropriate medical care arranged as appropriate and with the permission of the volunteer. Decisions to exclude the volunteer from enrolling in the trial or to withdraw a volunteer from the trial will be at the discretion of the Investigator.

# 10.8 Local Safety Monitor

The LSM will be appointed to provide real-time safety oversight. The LSM will review SAEs deemed possibly, probably or definitely related to study interventions. The LSM will be notified within 24 hours of the Investigators' being aware of their occurrence. The LSM has the power to terminate the study if deemed necessary following a study intervention-related SAE. At the time of writing, the LSM is [name], a Clinical Tutor in Medicine, Honorary Consultant Physician and Director, Centre for Tropical Medicine at the University of Oxford. All correspondence between the Investigator and the LSM will be conveyed by the Investigator to the trial Sponsor on their request.

The LSM may be contacted for advice and independent review by the Investigator or trial Sponsor in the following situations:

- Following any SAE deemed to be possibly, probably, or definitely related to a study intervention
- Any other situation where the Investigator or trial sponsor feels independent advice or review is important.

The study can be put on hold upon advice of the LSM, CI, study sponsor or Ethical Committee(s), for any single event or combination of multiple events which, in their professional opinion, jeopardise the safety of the participants or the reliability of the data. If the study is placed on hold it may only be restarted following discussion with and approval from the LSM, the ethics committee(s), the trial Sponsor, the MHRA and CI.

